11.1 Adverse events

Adverse events (AE) will be coded using MedDRA, and the National Cancer Institute Common Terminology Criteria for AEs (CTCAE criteria v5.0 or higher). They will be presented by primary System Organ Class (SOC) and Preferred Term (PT), or by PT only (in descending order) by dose cohort and overall. Subjects will be summarized at most one time per SOC and at most one time per PT, unless otherwise specified.

Adverse events are collected from the first GEN3009 dose until 30 days after the last GEN3009 dose. Treatment-emergent adverse events (TEAEs) are defined as AEs which begin, or worsen, during the on-treatment period ending 4 weeks after the last dose of trial medication as defined in Section 5.4. Adverse events collected during the post-treatment period will be flagged in data listings, and excluded from summaries, and will not be categorized as TEAEs.

The following summaries of TEAEs will be presented:

- All TEAEs, by SOC and PT
- All TEAEs, by PT, in order of descending frequency
- Serious TEAEs adverse events (SAEs), by SOC and PT
- Non-serious TEAEs, by SOC and PT
- TEAEs of CTCAE grade 3 or higher, by SOC and PT
- Non-serious TEAEs of CTCAE grade 3 or higher, by SOC and PT
- Related non-serious TEAEs of CTCAE grade 3 or higher, by SOC and PT
- TEAEs leading to dose reduction or dose interruption, by SOC and PT
- TEAEs leading to permanent discontinuation of trial treatment, by SOC and PT
- TEAEs by SOC, PT, and severity, where subjects are presented at the highest recorded severity level within SOC and PT
- Related TEAEs, by SOC and PT
- Related serious TEAEs, by SOC and PT
- TEAEs by SOC, PT, and relationship, where subjects are presented at the highest recorded relationship within SOC and PT

- Fatal TEAEs

The following tables will also be presented by overall ADA status, as per Section 11.8.

- Non-serious TEAEs of CTCAE grade 3 or higher, by SOC and PT
- Fatal TEAEs

All adverse events will be listed by subject, with those beginning during the post-treatment period flagged. Additional listings will be presented for all SAEs, all AEs leading to withdrawal of treatment, non-serious AEs of grade 3 or higher, and fatal AEs.

In addition, adverse events will be presented graphically by the incidence of AEs over infusion number, and using a swim lane plot to monitor the severity of AEs over time.

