11.4.1 Primary Endpoints

11.4.1.1 Escalation and Safety Run-in in Expansion

11.4.1.1.1 DLTs and AEs

- Number of DLTs during the DLT period (initial 28 days of treatment).
- Summary tables for AEs will include only AEs that started or worsened during the on-treatment period (the TEAEs).
- The incidence of TEAEs (new or worsening from baseline) will be summarized by system organ class and/or preferred term, severity (CTCAE grade), type of AE, and relationship to GEN3009 (Dose Escalation) or GEN3009 + GEN3013 (safety run-in).
- SAEs, non-serious AEs, and AESIs during the on-treatment period will be tabulated.
- All deaths (on treatment and post treatment) will be summarized.
- All AEs, deaths and SAEs (including those from the pre and post-treatment periods) will be listed and those collected during the pre-treatment and post-treatment periods will be flagged.

Further summaries of AEs will be specified in the SAP.

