- The pre-treatment period includes information collected from the date of informed consent until the day prior to the first dose of trial medication. (Subjects not receiving trial medication will remain in the pre-treatment period for the duration of their participation.)
- The on-treatment period begins on the date of the first dose of trial medication, and stops 4 weeks (i.e. 28 days) after last dose of trial medication.
- The post-treatment period begins at end of on-treatment period + 1 day

If incomplete data makes it impossible to definitively assign an observation to one of these periods, the data will be conservatively assigned to the on-treatment period.

Definition of analysis time points or time windows

Data reported on the CRF will be assigned to analysis visits as follows, where 'visit' refers to visit name or cycle day, as applicable. Data will be listed by nominal visit, as recorded on the CRF, and summarized in tables and figures using the analysis day:

- a) Visits prior to the date of first dose of trial medication will be assigned to the Screening visit.
- b) Scheduled post-baseline visits other than end of treatment or end of trial visits will be assigned to the nominal visit.
- c) Regularly scheduled assessments occurring at an unscheduled visit, end of treatment visit, or end of trial visit will be assigned to the closest scheduled visit (or the later of the two visits, if equidistant between scheduled visits). For example, if a subject completes Cycle 3 Day 8 visit and returns 2 days later for an end of treatment visit, the assessments collected at that visit would be assigned to Cycle 3 Day 11.
- d) If >1 assessment of a certain type is assigned to a given analysis visit:
 - i. If only 1 assessment is non-missing, the non-missing results will be summarized.
 - ii. If >1 assessment is non-missing, and only 1 assessment is within the visit window, the assessment within the visit window would be summarized.
 - iii. If >1 non-missing assessments are within the visit window, and one was collected at the actual visit, that assessment will be used. Otherwise, the one that is closest to the planned time of the visit will be used.

5.9 *Multiple Comparison/Multiplicity*

No multiplicity adjustment is planned.

6 Subject Accounting and Disposition

6.1 *Subject accounting*

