10.3.2 Measurable and Non-Measurable Lesions

All measurable and non-measurable lesion results will be listed.

The sum of the products of the perpendicular diameters (SPD) for measurable lesions will be included in listings, as well as summarized by visit and best (greatest) reduction per subject. SPD will also be summarized by ADA subgroup, as described in Section 11.8.

Changes in SPD for measurable lesions will also be presented graphically as follows:

- Mean + SE plots over time for actual values
- Mean + SE plots over time for percent change from baseline
- Waterfall plot of best (greatest) reduction per subject
- Individual profile plots of the cross-products of the measurements of each lesion, over time

11 Safety

The primary endpoints for the Dose Escalation part include the number of DLTs during the DLT observation period, the frequency and severity of AEs and SAEs, changes from baseline in laboratory results, and changes from baseline in vital signs. The frequency and severity of AEs and SAEs and the changes from baseline in laboratory results and vital signs are secondary endpoints for the Dose Expansion part.

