11.1.3 Deaths and Fatal AEs

Fatal adverse events will be summarized by dose level cohort or diagnosis cohort (as appropriate), SOC, and PT. All fatal adverse events will be presented in a separate listing, with post-treatment AEs flagged.

All deaths will be summarized by cohort, period (on-treatment or post-treatment), and primary cause of death. Death information will be listed by subject as well.

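### For GEN3009 monotherapy, AEs are collected to day 30 after the last dose but count as treatment-emergent only to day 28, so AEs on days 29-30 drop out of the TEAE tables

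*SAP*

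**What the plan says.** SAP 11.1 sets out three rules one after another.

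- Collection: "Adverse events are collected from the first GEN3009 dose until 30 days after the last GEN3009 dose".
- Treatment-emergent status: an AE must begin or worsen "during the on-treatment period ending 4 weeks after the last dose of trial medication as defined in Section 5.4".
- Everything later: "Adverse events collected during the post-treatment period will be flagged in data listings, and excluded from summaries, and will not be categorized as TEAEs".

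The on-treatment period is defined under Trial periods in SAP 5.8: it "stops 4 weeks (i.e. 28 days) after last dose of trial medication", and the post-treatment period starts the next day. Section 5.4, which SAP 11.1 cites, covers durations and times to events and does not define this period. SAP 11.3.1 uses the same period for laboratory data and cites 5.8 correctly.

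The introduction to SAP 11 names as primary endpoints of Dose Escalation, besides DLTs, "the frequency and severity of AEs and SAEs, changes from baseline in laboratory results, and changes from baseline in vital signs". The same AE, laboratory and vital-sign measures are secondary in the Dose Expansion part.

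Protocol 11.4.1.1.1 restricts AE summary tables to events in the on-treatment period but gives that period no length. It lists all AEs, and "those collected during the pre-treatment and post-treatment periods will be flagged". For monotherapy, the current protocol also runs AE reporting to day 30 (Tables 3 and 6, footnote f; Section 10.2).

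**The concern.** The collection window and the analysis window are two days apart, and neither document says why. Sites are asked to record AEs through day 30. The last two days of that record cannot enter any TEAE table, including those for serious, grade 3 or higher, related and fatal events.

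The loss runs one way. Percentages use the cohort size as denominator (SAP 5.1), which the window does not change, so leaving events out can only reduce the number of subjects with a given TEAE. In the tables by severity or relationship, it can leave a subject in a lower category than the collected data support. For a first-in-human trial whose primary endpoints include AE frequency and severity, an unexplained cut in the favourable direction should be removed or justified.

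The wrong cross-reference adds a practical risk. A programmer who follows it to Section 5.4 finds treatment-duration formulas that add 7, 14 or 28 days depending on the cycle, and no on-treatment definition.

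**Working it through.** **Inputs**

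- End of AE collection: final GEN3009 dose + 30 days (SAP 11.1).
- End of the on-treatment period: final dose + 28 days (SAP 5.8).
- Start of the post-treatment period: the following day, final dose + 29 (SAP 5.8).
- Dosing: 28-day cycles, weekly in Cycles 1-3, every two weeks in Cycles 4-9, every four weeks from Cycle 10 (SAP 3.5).

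**The plan's own figure.** 4 weeks x 7 = 28 days, which agrees with SAP 5.8.

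**The gap.** 30 - 28 = 2 days, namely days 29 and 30. That is 2/30 = 6.7% of the follow-up days after the final dose.

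**Share of the whole collection period.** If the final dose falls on study day L, collection covers L + 30 days and the share left out is 2/(L + 30). With no dose delays:

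- Final dose C1D1: L = 1; 2/31 = 6.5%.
- Final dose C1D22: L = 22; 2/52 = 3.8%.
- Final dose C3D22: L = 2 x 28 + 22 = 78; 2/108 = 1.9%.
- Final dose C9D15: L = 8 x 28 + 15 = 239; 2/269 = 0.7%.

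**Why these are upper bounds.** Under Protocol 10.2, AE documentation stops earlier on new anti-cancer treatment, withdrawal of consent or death. A subject who reaches one of these by day 28 contributes neither day. SAP 11.1 also counts a subject once per SOC and once per PT. A late event therefore changes a table only if it is a new PT or SOC for that subject in that table, or carries a higher grade or relationship than one already counted. The documents give no AE onset times, so the number of omitted events cannot be computed.

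**What is not affected**

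- DLTs. The DLT period ends at C1D28 (SAP 5.8). The on-treatment period cannot end before study day 1 + 28 = 29, so no DLT-period event is cut off.
- Infusion-related reactions. Their onset is by definition within 24 hours of the infusion's end (SAP 11.1.2.1).
- Observations too incompletely dated to place in a period: "the data will be conservatively assigned to the on-treatment period".
- Deaths: "All deaths will be summarized by cohort, period (on-treatment or post-treatment), and primary cause of death".

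**The case against.** The best defence is that this is a disclosed choice. The two windows and the handling of later events stand in consecutive sentences. The protocol limits AE tables to the on-treatment period, sets no length for it there, and expects events outside it to be listed and flagged. Twenty-eight days also fits the SAP's own time structure: it is the cycle length and the longest dosing interval, and cycle day is undefined more than 28 days after the final dose. Finally, the SAP is written to protocol v4.0, which is not available here and may have explained the figure.

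Much of this stands. No protocol rule is broken, and the two SAP sentences do not contradict each other. But the cycle length is never offered as the reason, and it does not explain why collection should outlast analysis by two days. The gap lies wholly within the SAP, so it does not depend on the protocol version.

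A reader might infer more than the documents support:

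- **That these AEs are lost.** They are not. They remain in the listings with a flag, and the deaths table covers both periods.
- **That everything recorded at the safety follow-up visit is excluded**, because the current protocol places that visit at day 30 with a +14-day window. It is not. The date of onset or worsening decides, so an AE that began by day 28 and was reported at that visit is still a TEAE.
- **That every subject loses two days.** Two is the maximum.
- **That the combination cohort loses far more**, because its AE collection runs longer. This SAP does not cover that cohort, so it sets no TEAE window for it.

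**Conclusion.** The point holds for GEN3009 monotherapy as a minor misalignment. AEs that begin or worsen on days 29-30 after the final dose are collected and listed but kept out of all TEAE summaries. The effect can only understate TEAE frequency or severity. It is at most two days per subject, or 0.7% to 6.5% of collection days in the worked cases, and the effect on reported rates is probably smaller because of earlier stopping and once-per-subject counting. Dose-escalation decisions based on DLTs are untouched, and no formal hypothesis is tested.

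This rests on reading the SAP windows literally, on no dose delays in the worked cases, and on the early-stopping rule of the current protocol applying to these subjects. The wrong reference to Section 5.4 needs correcting whichever window is kept.

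**What to change.** In SAP 11.1, define a TEAE as any AE whose onset or worsening falls between the first dose and day 30 after the final GEN3009 dose, the same span as collection. Key the exclusion from summaries to that window, so that an event cannot be both a TEAE and excluded as post-treatment. Replace the reference to Section 5.4 with Section 5.8, or with the window as stated in 11.1.

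The cost is one derivation and SAP wording, with no new data. TEAE rates may come out slightly less favourable. The side effects depend on where the change is made:

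- **In 11.1 only.** The AE and laboratory windows then differ by two days, and the AE window runs past the on-treatment period in 5.8. The SAP should say so.
- **In 5.8.** The windows stay common, but deaths on days 29-30 move from post-treatment to on-treatment. The post-baseline laboratory window (SAP 11.3.1), with its worst grades and shift tables, lengthens by two days. So do the other summaries presented by period: vital signs, ECG, ECOG and constitutional symptoms.

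Changing 11.1 alone disturbs less.

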6.3 Management of Infusion-Related Reactions

IRRs can occur with GEN3009 administration. All patients must receive premedication for IRRs as described in Section [6.2.1](#).

Table 24 GEN3009 Dose Modification Rules for IRRs

IRR Grade	Dose Modification
Grade 1 or 2	
Stop GEN3009 infusion immediately and treat the subject based on local institutional guidelines.Once reaction symptoms resolve, resume the infusion at no more than half the rate at which the IRR occurred.If the subject does not experience any further IRR symptoms, infusion rate escalation may resume at increments and intervals as clinically appropriate. 
Please refer to Section 6.2.1 for premedication instructions.

Grade 3	
Stop GEN3009 infusion immediately and treat the subject based on local institutional guidelinesOnce reaction symptoms resolve, resume the infusion at no more than half the rate at which the IRR occurred.If the subject does not experience any further IRR symptoms, infusion rate escalation may resume at increments and intervals as clinically appropriate.If, after resumption of the infusion, symptoms return (irrespective of grade), permanently discontinue administration of GEN3009 and manage the IRR symptoms accordingly. 
Please refer to Section 6.2.1 for premedication instructions.

Grade 4 (life-threatening)	
Permanently discontinue administration of GEN3009 and institute appropriate emergency care.

Trained trial staff should be prepared to intervene in case of any IRRs occurring, with resources necessary for resuscitation (eg, agents such as epinephrine and aerosolized bronchodilator, also medical equipment such as oxygen tanks, tracheostomy equipment, and a defibrillator) available.

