10.1.2 Definition of Serious Adverse Events

An SAE is defined as an AE that meets 1 of the following criteria:

- Is fatal or life-threatening¹
- Results in persistent or significant disability/incapacity
- Constitutes a congenital anomaly/birth defect
- Is medically significant, ie, defined as an event that jeopardizes the subject or may require medical or surgical intervention to prevent 1 of the outcomes listed above. Medical and scientific judgment must be exercised in deciding whether an AE is “medically significant”
- Requires inpatient hospitalization or prolongation of existing hospitalization² (Planned hospitalization for observation following GEN3009 and/or GEN3013 (GEN3009 + GEN3013 cohort 4 only) administration during Cycle 1 should not be reported as an SAE).

¹The term “life-threatening” in the definition of “serious” refers to an event in which the subject was at risk of death at the time of the event; it does not refer to an event which hypothetically might have caused death if it were more severe.

²Hospitalizations for the following reasons should not be reported as SAEs:

- Routine treatment or monitoring of the underlying disease, not associated with any deterioration in the condition
- Solely due to progression of the underlying cancer
- Elective or pre-planned treatment for a pre-existing condition that is unrelated to the underlying disease and has not worsened since signing the informed consent
- Social reasons and respite care in the absence of any deterioration in the subject’s general condition
- Treatment on an emergency outpatient basis that does not result in hospital admission and involves an event not fulfilling any of the definitions of an SAE given above is not an SAE.

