11.7 Immunogenicity of GEN3009/GEN3013

Immunogenicity analysis samples will be scored ADA positive or ADA negative and subsequently reported. From positive ADA samples, titer values and neutralizing antibody scores (positive or negative) will be determined and reported. ADA negative samples with drug on board above the drug tolerance limits of the ADA method will be scored inconclusive due to possible drug interference. The association between positive/non-positive ADA and PK (predose, AUC, C_{max}), major safety signals (CTCAE \geq Grade 3) and efficacy information (change in tumor size by CT scan) may be explored.

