5.5 Covariates and strata

Diagnosis cohort (DLBCL, FL, CLL/SLL) will be used as a covariate for analyses that are pooled across diagnosis cohorts in the Dose Expansion part, where appropriate.

The following covariates may be summarized and/or used in analyses as appropriate:

- Diagnosis cohort (DLBCL, HGBCL, PMBCL, FL, MCL, MZL, SLL, or CLL for Dose Escalation part; DLBCL, FL, or CLL for Dose Expansion part)
- Age (continuous or <65 vs. 65+ years)
- Race (categorized into no more than 4 groups, such as Caucasian, Asian, Black, or Other)
- Eastern Cooperative Oncology Group (ECOG) score at screening (actual score or 0-1 vs. 2-4)
- Presence of constitutional symptoms at Screening
- Body mass index (BMI) at screening (continuous or categorized as <18.5, 18.5-24.9, 25.0-29.9, and 30.0+)
- Number of prior anti-cancer therapies (categorized as 1, 2, 3, 4+, or grouped into smaller categories)
- Time from last anti-CD20 therapy till first dose of GEN3009, in days
- Geographic location, as summarized below
- Prior CAR-T exposure category (exposure vs. no exposure)
- Overall MRD negativity status, as described in Section 5.2.4.
- Overall presence or absence of anti-drug antibodies, as described in Section 11.8
- Presence or absence of anti-drug antibodies at Baseline
- Refractory or relapsed to the last line of prior anti-lymphoma therapy
- Refractory or relapsed to the most recent prior anti-CD20 therapy
- Refractory or relapsed to the most recent prior anti-CD20 therapy, when that is the most recent prior anti-lymphoma therapy

- Prior autologous stem cell transplant status

Missing values of covariates will not be imputed. Subjects will be excluded from subgroup analyses, etc. as appropriate.

Trial sites, countries and regions

Subjects will be recruited from across Europe and North America.

Trial sites or countries will be pooled to main regions and regions using the "Standard Country or Area Codes for Statistical Use provided by the Statistics Division of the United Nations Secretariat" [1] as per Appendix II.

In general, Main Region may be used as a covariate. Region may also be considered as a covariate. Regions with <5 subjects will be combined within Main Region, combining the smallest regions with others the same size, and the next larger size if necessary, until each region or pooled region has 5 or more subjects.

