12.2 Protein Expression

CCI

13 Pharmacokinetic (PK) Analyses

Venous blood samples are collected prior to GEN3009 dosing, and specified time points after dosing, as described in Table 1-3 (Dose Escalation), Table 1-6 (Dose Expansion) and Section 9.5 of the protocol, for the measurement of plasma concentrations of GEN3009. Samples will also be collected at the End of Treatment visit.

The concentration of GEN3009 in plasma samples will be determined by a validated, specific, and sensitive ligand binding assay, at the assay CRO.

13.1 *The PK analysis and output to be generated are detailed in the next paragraphs. In short, GEN3009 concentration data will be presented graphically and summarized by dose group and ADA status. The sponsor will calculate PK parameters based on non-compartmental methods and will provide the results to be included in the Tables, Listings and Figures as part of this SAP. Graphical exploration of the relationships between exposure and covariates, observations of safety, efficacy or pharmacodynamic biomarkers will be performed by the sponsor outside of the scope of this SAP. GEN3009 Concentration data*

Individual observations of plasma concentration will be listed chronologically for each subject. Concentrations below the lower limit of quantification (LLOQ) will be reported as <LLOQ in data listings and omitted from summary statistics and graphs.

GEN3009 concentration data will be presented graphically, using individual curves of concentrations. All available data will be shown in these figures. Separate figures will be presented showing the plasma concentration-time profiles after the first dose of Cycle 1 and Cycle 2.

Concentrations will be summarized using both arithmetic and geometric means, standard deviations, coefficient of variations expressed as percentages (CV%), medians, minimums and maximums. Summaries will be presented overall and by ADA status, as described in Section 11.8.

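### The adverse event tables split by ADA status leave out serious, non-fatal Grade 3–4 events

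*SAP*

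**What the plan says.** SAP 11.1 sets out 14 TEAE summaries. Among them are all serious TEAEs, all TEAEs of Grade 3 or higher, the non-serious subset of those, and fatal TEAEs. It then adds: "The following tables will also be presented by overall ADA status, as per Section 11.8". Two entries follow. The first is "Non-serious TEAEs of CTCAE grade 3 or higher, by SOC and PT"; the second is fatal TEAEs.

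SAP 11.8 derives overall ADA status as positive, negative or indeterminate, and plans listings and counts of ADA results. It adds no adverse event table. Two other sections commit to non-safety outputs by ADA status: lesion size in SAP 10.3.2 ("SPD will also be summarized by ADA subgroup, as described in Section 11.8") and drug concentrations in SAP 13.1 ("Summaries will be presented overall and by ADA status, as described in Section 11.8"). SAP 13.2 does the same for the PK parameters. In SAP 5.5, ADA status is only one of a list introduced by "The following covariates may be summarized and/or used in analyses as appropriate". SAP 5.6 allows those covariates in exploratory subgroup analyses in Dose Expansion if numbers permit.

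Protocol 11.7 describes what may be explored against ADA as PK, "major safety signals (CTCAE" Grade 3 or higher), and change in tumor size. It does not restrict the safety part to non-serious events.

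**The concern.** The two tables take the ends of the Grade 3-or-higher range and leave out the middle. A non-serious Grade 3 event is compared by ADA status and so is a death, but a life-threatening event that the subject survives is not. No reason is given for the exclusion.

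Immunogenicity is a secondary objective in both parts of the trial (SAP 3.2). With cohorts this small, a few serious events could be the whole signal. The ADA columns could look alike in the planned tables while the serious non-fatal events differ between them, and a reader of those tables would have no sign that anything was missing.

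**Working it through.** No arithmetic beyond counting applies. The check divides all Grade 3-or-higher TEAEs by grade, seriousness and outcome, and asks which ADA-split table would hold each type.

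**Inputs**

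- Table A (SAP 11.1): TEAEs that are both non-serious and Grade 3 or higher.
- Table B (SAP 11.1): fatal TEAEs.
- Seriousness (protocol 10.1.2): an event is serious if it "Is fatal or life-threatening", and also if it requires inpatient hospitalization, apart from planned Cycle 1 observation and the other listed exceptions. Every fatal event is therefore serious.
- Grade and seriousness are separate attributes: protocol 10.4.1 speaks of Grade 3 and 4 laboratory values being reported as serious only if they are judged to be so.

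**Coverage**

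| Type of Grade ≥3 TEAE | Table A | Table B | Shown by ADA status |
|---|---|---|---|
| Non-serious, Grade 3 | yes | no | yes |
| Non-serious, Grade 4 | yes | no | yes |
| Serious, non-fatal, Grade 3 | no | no | **no** |
| Serious, non-fatal, Grade 4 | no | no | **no** |
| Fatal | no | yes | yes |

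Three of the five types are covered and two are not. Grouped as non-serious, serious non-fatal and fatal, two of three groups are covered.

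**Events in the missing group**

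- Protocol 6.3, Table 24, labels the top grade of infusion-related reaction "Grade 4 (life-threatening"). Such a reaction is serious under protocol 10.1.2. If the subject survives, it is in neither table.
- A Grade 3 event that leads to an unplanned admission is serious and non-fatal, so it is in neither table.

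**Does another output fill the gap?** The unredacted SAP commits to five outputs by ADA status: Table A, Table B, lesion size (10.3.2), concentrations (13.1) and PK parameters (13.2). The last three are not safety outputs, so none of the five holds the missing group. The covariate and subgroup provisions of SAP 5.5 and 5.6 are optional and name no adverse event table.

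**After the change.** Putting the summary of all Grade 3-or-higher TEAEs in place of Table A covers five of the five types.

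**The case against.** The strongest reply concerns importance, since the omission itself is plain from the text.

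- **Nothing required is breached.** The protocol's immunogenicity endpoint is the incidence of neutralizing antibodies, and protocol 11.7 says only that an association with safety may be explored. The SAP is also written to protocol version 4.0 (SAP 1.1), whereas the protocol supplied is version 7.0, so 11.7 cannot show a departure from the text the SAP followed. Both points stand. Protocol 11.7 is supporting context here; the gap follows from SAP 11.1 alone.
- **The data are not lost.** The events remain in the overall serious and Grade 3-or-higher tables. Serious events are listed by subject, and ADA results by subject and time point. With at most 20 subjects per indication, a reader could match the two by hand. That is true, but the SAP does not say that the adverse event listings carry ADA status, and the purpose of an ADA-split table is to spare the reader that step.
- **Counts will be sparse.** Up to 20 subjects across three ADA categories, then split by system organ class and preferred term, gives thin tables either way, and no hypothesis is tested. This also stands, but it applies equally to the two tables the SAP already commits to.
- **Infusion-related reactions are a weak example.** Protocol 2.1.4.1 reports that they mostly came with the first infusion and were mostly Grade 1 or 2. Antibodies induced by treatment cannot precede the first infusion, and overall ADA status takes no account of timing. This limits what the comparison can say about cause and suggests that few such reactions would be affected. It does not explain why serious non-fatal events of every kind are left out.
- **The output list is not final.** SAP Appendices III to V are to be produced later. The omission, however, is in the body of the SAP, from which those lists would be drawn.

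**Conclusion.** The concern holds. Followed as written, SAP 11.1 gives an ADA safety comparison that omits every serious, non-fatal Grade 3–4 TEAE, which is one of the three groups that make up Grade 3 or higher. None of the five outputs committed by ADA status supplies it.

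The conclusion rests on the plain definitions of the two tables and on the protocol's definition of a serious event. It assumes that no redacted text holds a further adverse event table by ADA status. The consequence is modest, because the tables are descriptive and no dose decision or primary endpoint depends on them. The change should be made because the omission is certain and the remedy costs almost nothing.

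**What to change.** In SAP 11.1, in the list of tables by overall ADA status, replace the entry "Non-serious TEAEs of CTCAE grade 3 or higher, by SOC and PT" with the summary of all TEAEs of Grade 3 or higher, serious and non-serious together, which the same section already plans. Keep the fatal TEAE table. It will overlap with the new one, but it shows deaths separately.

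An alternative is to keep the present entry and also split the planned serious TEAE table by ADA status. That closes the same gap and also brings in serious Grade 1–2 events, at the price of one more table.

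The replacement is a change of SAP wording: one planned table is run by ADA status in place of another. It needs no new data and no protocol change.
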